## Study endpoints:

The primary outcome (actigraphically-derived total sleep time) and all secondary and exploratory measures are continuous variables. Primary analyses will focus on the difference from the baseline total sleep time (in minutes) to the total sleep time evaluated in each of the two treatment periods, within subjects. The key secondary variables are the difference from baseline to the end of each treatment period are actigraphically-derived wake after sleep onset and self-reported ISI.

Exploratory analyses will similarly focus on the differences from the baseline value to the final observed value at the end of each treatment period. As these are exploratory analyses, no p-values will be determined other than as described below in the hierarchical testing. These endpoints include:

a) Diary-derived wake after sleep onset

- b) Diary-derived total sleep time
- c) Diary-derived SOL, sleep efficiency and sleep quality
- d) RLS severity via IRLS

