## Secondary Aims:

- To determine whether suvorexant will have significantly greater effect than placebo in reducing actigraphically-derived wake after sleep onset (WASO) in patients with effectively treated RLS with persistent insomnia.
- To determine whether suvorexant will have significantly greater effect than placebo in decreasing Insomnia Severity Index (ISI) scores in patients with effectively treated RLS with persistent insomnia.

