## **Exploratory Aims:**

- To determine whether suvorexant will have significantly greater effect than placebo for self-reported sleep metrics (e.g., quality, disturbance, sleep latency and duration) in patients with effectively treated RLS with persistent insomnia.
- To determine whether suvorexant will have an effect on RLS severity in patients with effectively treated RLS with persistent insomnia.

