## **Overview of analytic plan:**

The primary hypothesis for this trial is that suvorexant is superior to placebo in reducing actigraphically-derived total sleep time in patients with persistent insomnia in the context of effectively treated restless legs syndrome. The primary endpoint is the change in actigraphically-derived total sleep time from baseline to the end of each 4-week treatment period. Key secondary endpoints include actigraphically-derived wake after sleep onset and self-reported ISI, and exploratory endpoints include subjective total sleep time and wake after sleep onset, and RLS severity.

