## STATISTICAL METHODS

Efficacy variables will be analyzed using an analysis of variance model with treatment, sequence, and period as fixed effects and subject within sequence as a random effect. Least squares (LS) mean treatment difference will be calculated from the model. Diagnostic methods will be used for all variables to assess their distributional assumptions and to examine potential outlying or influential data points. This analytical method will similarly be used to assess secondary outcomes. Within-treatment changes from baseline will also be evaluated using a paired t-test for the primary and secondary efficacy variables of change from baseline in total sleep time, wake after sleep onset, and ISI.

The primary outcome analysis will use the intention-to-treat principle and include all participants who received at least one dose of study medication and completed at least one week of sleep diaries following randomization.

Per-protocol analyses will be repeated on the subgroup of subjects that achieve 85% medication adherence based on the number of pills returned at the end of study. Variables related to subjective total sleep time will be determined by Pearson correlation and simple regression analysis using weighted least squares. A two-sided P value <0.05 will be considered significant.

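### The plan defers exploratory p-values to a hierarchical test it never describes, and WASO and ISI default to the general two-sided 0.05 with no gate, order or level of their own

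*Combined protocol and SAP*

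**What the plan says.** The sentence at issue is in section IX, Study endpoints. It introduces the exploratory list (diary measures and RLS severity by the IRLS) and says that "no p-values will be determined other than as described below in the hierarchical testing".

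What follows it is Statistical Methods, Power/Sample Size and the references. Statistical Methods describes the crossover analysis of variance, from which "Least squares (LS) mean treatment difference will be calculated from the model". Of the secondaries it says: "This analytical method will similarly be used to assess secondary outcomes". It gives one significance rule: "A two-sided P value <0.05 will be considered significant". Power/Sample Size deals only with TST.

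The Overview of analytic plan gives the secondaries their rank: "Key secondary endpoints include actigraphically-derived wake after sleep onset and self-reported ISI". Section II poses each as a significance question. For WASO, the aim is to find out whether suvorexant has a "significantly greater effect than placebo in reducing actigraphically-derived wake after sleep onset (WASO)". For ISI, it is whether suvorexant has a "significantly greater effect than placebo in decreasing Insomnia Severity Index (ISI) scores". The first exploratory aim uses the same form: "significantly greater effect than placebo for self-reported sleep metrics (e.g., quality, disturbance, sleep latency and duration)".

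**The concern.** The plan points to a testing procedure that is not there, which leaves two gaps.

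The direct gap concerns the exploratory endpoints. The default is no p-values, with an exception defined by the missing hierarchy. The first exploratory aim nevertheless asks a significance question about self-reported sleep, and only that exception could answer it. An analyst cannot tell from the plan whether any exploratory endpoint may be tested, or which.

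The second gap concerns WASO and ISI. Both are called key, both aims are worded as significance claims, and both use the primary model. Nothing makes their tests depend on TST, puts one before the other, or sets a level for the pair. Followed literally, the plan allows either to be claimed at 0.05 whatever the other tests show. An order or gate could also be supplied after the results are known and presented as the hierarchy the plan had in mind.

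**Working it through.** **1. Search for the hierarchy.** The term occurs once, in the sentence quoted. Neither Statistical Methods nor Power/Sample Size names a gate, an order, a split of alpha or an adjustment. WASO comes before ISI in Secondary Aims, in the Overview and in Study endpoints, but none of these calls the listing a testing order. Section numbers jump from IX to XI, but the text between the endpoint list and the references is continuous and shows no redaction, so a lost page does not explain the gap.

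**2. Reproduce the plan's own figure.** Power/Sample Size gives effect size 0.58, two-sided 0.05, 90% power and 34 subjects. For a within-subject comparison:

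- noncentrality = 0.58 × √34 = 3.382
- power from the noncentral t with 32 degrees of freedom = 0.906
- with n − 1 degrees of freedom, power is 0.898 at n = 33 and 0.907 at n = 34, so 34 is the smallest sufficient number
- 44 randomized × (1 − 10/44) = 34 evaluable

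The figure reproduces. The sample size rests on one test, TST at two-sided 0.05.

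**3. Error under the default rule.** Assume neither secondary is affected and each is tested at 0.05.

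- Correlation 0: 1 − 0.95² = 0.0975
- Correlation 0.3, 0.5, 0.7, 0.9: 0.095, 0.091, 0.084, 0.070
- Only one of the two nulls true: 0.050 at any correlation, because only one false claim is possible

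**4. Error under candidate rules.** Both secondary nulls are again true, and TST truly works with power 0.906. The three test statistics are taken as normal with one common correlation (2,000,000 simulated draws per cell). Holm requires the larger |z| to exceed 2.241, then the other to exceed 1.960.

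| Rule | Corr. 0 | Corr. 0.5 | Corr. 0.9 |
|---|---|---|---|
| As written (no gate) | 9.75% | 9.1% | 7.0% |
| TST gate only, both at 0.05 behind it | 8.8% | 7.2% | 3.8% |
| TST, then WASO, then ISI | 4.5% | 3.9% | 2.7% |
| TST gate, then Holm on WASO and ISI | 4.5% | 3.6% | 1.9% |

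The entries at correlation 0 can be checked by hand:

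- gate only: 0.906 × 0.0975 = 0.088
- fixed sequence: 0.906 × 0.05 = 0.0453
- gated Holm: 0.906 × 0.0494 = 0.0448

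A gate alone is therefore not enough. The last two rules stay at or below 5% whatever the TST effect.

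**5. Power given up.** The documents give no power for the secondaries, so the stand-alone values are assumptions. Ranges run from correlation 0 to 0.9.

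| Stand-alone power | Fixed sequence | Gated Holm |
|---|---|---|
| WASO 80%, ISI 80% | WASO 73–79%, ISI 58–75% | 70–75% each |
| WASO 50%, ISI 80% | ISI 36–50% | ISI 68–71% |

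Check at correlation 0, fixed sequence: WASO 0.906 × 0.80 = 0.725; ISI 0.906 × 0.80 × 0.80 = 0.580.

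**The case against.** The strongest reply is that the sentence is about exploratory endpoints only and restricts p-values rather than promising control elsewhere. That is correct. A reader might infer that the sponsor committed to a hierarchy over WASO and ISI and then left it out. The text does not say so; it supports only the inference that some ordered testing was intended.

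A second reply is that a level is stated. It is: the two-sided 0.05 is general and applies to the secondaries. What is missing is a gate, an order, or a level specific to them.

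Third, a small trial with one primary endpoint need not control error over its secondaries, and nothing in the documents promises that it will. This stands as far as it goes. No particular rule is compelled, and openly unadjusted p-values would also be coherent. But the aims ask for significant effects on WASO and ISI, and the plan mentions hierarchical testing, so it should state which approach it takes.

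Fourth, the size depends on both secondary nulls being true. The Background describes suvorexant as helping chiefly by shortening nocturnal awakenings and lengthening sleep, so TST working while WASO does not may be an unlikely case. A single common correlation across two actigraphic measures and a questionnaire is also a simplification. Both points limit the size but do not remove the gap.

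**Conclusion.** The point holds in this form. The hierarchy is cited but absent, so the status of exploratory p-values is undefined, and WASO and ISI fall to the general two-sided 0.05 with nothing linking them to TST or to each other. If both secondary nulls are true, the chance of at least one false claim is 7.0% to 9.75% over an assumed correlation of 0.9 to 0. If only one is true, there is no excess over 5%.

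A reader might go further and conclude that the trial's overall type I error is inflated, since three independent null tests at 0.05 give 1 − 0.95³ = 14.3%. The documents do not support that as a criticism of the main result. There is a single primary endpoint with its own 5%, and the 34 evaluable subjects are justified for it alone. The exposure is confined to claims on WASO and ISI and to any exploratory p-value. This should be fixed before unblinding, but it does not threaten the primary conclusion.

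**What to change.** Before unblinding, add one of these rules to Statistical Methods:

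- **Fixed sequence.** TST at two-sided 0.05; WASO at 0.05 only if TST is significant; ISI at 0.05 only if WASO is significant. This follows the order of listing, which the plan would then have to declare as the testing order.
- **Gated Holm.** TST at two-sided 0.05; if significant, compare the smaller of the WASO and ISI p-values with 0.025 and, if that succeeds, the other with 0.05. ISI then does not depend on WASO.

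In Study endpoints, delete the exception, so that exploratory endpoints are reported as estimates with 95% confidence intervals unless named in the sequence. Reword the first exploratory aim to match.

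If the sponsor does not want control over the secondaries, the minimum is to delete the reference to hierarchical testing and label the WASO and ISI p-values as unadjusted and not confirmatory.

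The change is to wording only: the TST level, the 34 evaluable subjects and the TST power of 0.906 stay as they are. The cost is the secondary power shown in the working. It is moderate under gated Holm, and it can be large for ISI under the fixed sequence if WASO is the weaker endpoint. If the sponsor doubts that WASO will be well powered, that favours Holm.

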## STATISTICAL METHODS

Efficacy variables will be analyzed using an analysis of variance model with treatment, sequence, and period as fixed effects and subject within sequence as a random effect. Least squares (LS) mean treatment difference will be calculated from the model. Diagnostic methods will be used for all variables to assess their distributional assumptions and to examine potential outlying or influential data points. This analytical method will similarly be used to assess secondary outcomes. Within-treatment changes from baseline will also be evaluated using a paired t-test for the primary and secondary efficacy variables of change from baseline in total sleep time, wake after sleep onset, and ISI.

The primary outcome analysis will use the intention-to-treat principle and include all participants who received at least one dose of study medication and completed at least one week of sleep diaries following randomization.

Per-protocol analyses will be repeated on the subgroup of subjects that achieve 85% medication adherence based on the number of pills returned at the end of study. Variables related to subjective total sleep time will be determined by Pearson correlation and simple regression analysis using weighted least squares. A two-sided P value <0.05 will be considered significant.

## **Power/Sample Size:**

Statistical power for the primary endpoint, actigraphically-assessed total sleep time, was estimated from pooled analyses of data from placebo-controlled clinical trials of suvorexant for the treatment of insomnia using polysomnographically-measured total sleep time. The difference between 15/20 mg suvorexant and placebo at 1 month in least squares mean change from baseline was 34.7 minutes (95% CI: 27.8, 41.5), corresponding to an effect size of 0.58. Although actigraphy is not identical to polysomnography, multiple studies (including one by our group and two using the Phillips Spectrum actiwatch) with insomnia patients demonstrate high correlations between these two objective recording methods for total sleep time, wake after sleep onset, and sleep efficiency, particularly when event markers are employed.

With an effect size of .58, 34 randomized subjects are required to achieve 90% power to detect a statistical significance level of 0.05. In total, we expect to randomize 44 participants to treatment to have 34 completed subjects with evaluable data.

